4.5 Patient Discontinuation/Withdrawal Criteria

Any patient who voluntarily withdraws consent or is discontinued (e.g., because of an AE) from the study prior to completion will be considered as withdrawn from the study. Patients may be discontinued from the study for any reason including any of the following circumstances:

- Occurrence of intolerable AE, as assessed by the Investigator or designee.
- Clinically significant abnormality on vital signs, electrocardiogram (ECG), clinical

laboratory, or physical examination evaluations, as assessed by the Investigator or designee.

- Subjects with a QTcF ≥ 500 msec or ≥ 60 msec above the patient's Baseline value will discontinue study medication and be re-assessed. The ECG should be repeated until values return below 500 msec, or ≥ 60 msec above Baseline. These findings will be reviewed by a cardiologist. Any additional intervention for the safety of the subject should be discussed with the Study Medical Monitor and Sponsor.
- ALT or AST ≥ 2 x ULN.
- Withdrawal of consent.
- Lost to follow-up.
- Administrative reasons (e.g., Sponsor decision).
- Major violation of the protocol.
- If in the opinion of the qualified Investigator, it is in the best interest of the patient.
- Non-compliance with study requirements and restrictions.
- Use of a concomitant medication that, in the opinion of the Investigator or designee, could interfere with the study procedures or data integrity or compromise the safety of the patient.
- Positive breath alcohol test at Check-in to the CRU.
- Termination of the study.

When an event such as a family emergency, a transient intercurrent illness (e.g., a cold) unrelated to study drug, or a remediable act of non-compliance prevents a patient from Check-in to the CRU, but the patient wishes to continue in the study, with the agreement of the Investigator, the research site staff may attempt to reschedule the Check-in and retain the patient in the study.

If a patient is prematurely discontinued from participation in the study for any reason after study drug administration, the Investigator or designee must make every effort to perform the assessments scheduled for the Day 14 visit (7 days after the last dose of study drug). The reason for withdrawal will be recorded in the eCRF and the patient's source medical record.

In the event of a patient discontinuation following dosing, PK and safety assessments may continue at the discretion of the Investigator based on the time points outlined in the Time and Events Schedule ([Table 1](#)).

Patients who are randomized, but not dosed, may be replaced. Patients who receive at least one dose of study drug, but are withdrawn prior to study completion, will not be replaced.

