Abbreviations: 4-Item PSRS = 4-Item Positive Symptom Rating Scale; AE = adverse event; ATRQ = Antidepressant Treatment Response Questionnaire; BMI = Body Mass Index; BP = Blood Pressure;; CADSS = Clinician Administered Dissociative States Scale; CGI-I = Clinical Global Impressions of Improvement; CGI-S = Clinical Global Impressions of Severity; COWS = Clinical Opiate Withdrawal Scale; CRU = Clinical Research Unit; C-SSRS = Columbia-Suicide Severity Rating Scale; CTNI = Clinical Trials Network and Institute; DNA = deoxyribonucleic acid; ECG = Electrocardiogram; EDP = End of the Dosing Period; EOP = End of the Observation Period (Day 14 ± 3 days); FSH = follicle stimulating hormone; FU = Follow-Up Visit (Day 21 ± 3 days); HAM-D-17 = Hamilton Rating Scale for Depression; HIV = Human Immunodeficiency Virus; HR = Heart Rate; MADRS = Montgomery-Asberg Depression Rating Scale; MGH = Massachusetts General Hospital; MINI = Mini International Neuropsychiatric Interview, Version 7.0.2; PK = Pharmacokinetics; QD = Quaque Die (Once Daily); RR = Respiratory Rate; SOP = Standard Operating Procedure; SDQ = Symptoms of Depression Questionnaire; SAFER = State versus trait; Assessability; Face validity; Ecological validity; and Rule of three Ps [pervasive, persistent, and pathological).

^a All Baseline/Day 1 assessments and activities will be done pre-dose, unless otherwise specified.

^b Review of Medical History for Status of Intercurrent Illnesses.

^c Vital signs include blood pressure (BP), heart rate (HR), pulse oximetry, and respiratory rate (RR) measured after the patient has been resting in a supine or semi-supine position for at least 3 minutes. Measurement of orthostatic BP should follow measurement of supine or semi-supine BP with patients asked to

stand for 3 minutes before measurement of orthostatic BP. From Day 2 through Day 7, vital signs will be measured once before the dose of study drug. Vital signs will be measured once on Day 8, Day 9 prior to Discharge and Day 14.

^d On Day 1 and Day 2, an ECG will be done 1 hour pre-dose and 2 hours, 4 hours, 6 hours, and 8 hours post-dose. From Day 3 through EDP (Day 7), an ECG will be done 2 hours after the dose of study drug. An ECG will also be done on Day 8, prior to Discharge on Day 9, and at EOP (Day 14).

^e Testosterone levels will be assayed for male patients on Day 1 and Day 7.

^f Urine drug screen tests for tetrahydrocannabinol, opiates (including oxycodone), amphetamines, cocaine, and benzodiazepines.

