4.3 Exclusion Criteria

Patients will not be considered eligible to participate in this study if any one of the following exclusion criteria is satisfied at Screening:

1. History or presence of clinically significant abnormality as assessed by physical examination, medical history, 12-lead ECG, vital signs, or laboratory values, which in the opinion of the Investigator would jeopardize the safety of the patient or the validity of the study results, including torsades de pointes, any bradyarrhythmias, or uncompensated heart failure.
2. Chronic use of prescribed opioids (i.e., >120 days in a 6-month period) up to 6 months prior to Screening or any recreational use of opioids.
3. Evidence of clinically significant hepatic or renal impairment, including alanine aminotransferase (ALT) or aspartate aminotransferase (AST) >1.5 x upper limit of normal (ULN), bilirubin >1 x ULN, or endocrine laboratory values (including clinically significant thyroid parameters, i.e., thyroid stimulating hormone [TSH], triiodothyronine [T3], and thyroxine [T4]).
4. History or family history of sudden unexplained death or long QT syndrome (measure of the time between the start of the Q wave and the end of the T wave in the heart's electrical cycle).
5. An average QTcF \geq 450 msec or an average QRS interval \geq 120 msec from the 12-lead ECGs performed at Screening.
6. History of clinically diagnosed hypotension requiring treatment.
7. History or presence of any condition in which an opioid is contraindicated (e.g., significant respiratory depression, acute or severe bronchial asthma or hypercarbia, bronchitis, or has/is suspected of having paralytic ileus).
8. No more than 3 prescribed doses of an opioid within the 6 months prior to Screening and no use at all within the last month.
9. Use of an antipsychotic, anticonvulsant, or mood stabilizer, regardless of indication, within the 3 months prior to Screening.

10. History of allergy or hypersensitivity to methadone or related drugs (e.g., opioids).
11. Positive test for hepatitis B or human immunodeficiency virus (HIV). Patients with a positive hepatitis C test may be considered for inclusion with approval from the Medical Monitor.
12. Any current and primary psychiatric disorder, as defined as a condition that is the primary focus of distress and/or treatment, other than MDD.

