6.1.4 Dosing Period (Day 1 to Day 7)

The dosing period will begin on Day 1 and continue through the last dose of study drug on Day 7 (End of the Dosing Period [EDP]). Study drug will be administered in the morning. Assessments during the dosing period will include measures of safety and tolerability, PK, and efficacy. For patients who discontinue study drug prior to Day 7, all EDP assessments should be completed according to the Time and Events Schedule (Table 1) provided informed consent has not been withdrawn.

6.1.5 24-Hour Post-Dose Assessments (Day 8)

On Day 8, patients will be evaluated 24 hours after the final dose of study drug on Day 7 according to the Time and Events Schedule (Table 1). Blood samples will also be drawn for PK analysis approximately 24 hours after the last dose of study drug.

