7.1.4 Other Adverse Events of Interest

If other AEs of interest are observed during the study, they will be recorded in the eCRFs and analyzed as appropriate in the final clinical study report. Examples of these types of AEs would be difficulty breathing, chest pain, or clinically significant bradycardia, tachycardia, or QTcF prolongation (≥ 500 msec or ≥ 60 msec above the patient's Baseline value that continuously occurs over a period of time). At the discretion of the Investigator, ECGs or other relevant tests may be repeated for confirmation of the results.

If more than one ECG is collected, the mean of the replicate measurements will be reported. If any of the 3 individual ECG tracings has a QTcF value ≥ 500 msec, but the mean of the triplicates is not ≥ 500 msec, the data from the subject's individual tracing will be described in a safety section of the study report to place the ≥ 500 msec value in appropriate clinical context. However, values from individual tracings within triplicate measurements that are ≥ 500 msec will not be included in the categorical analysis unless the average from those triplicate measurements is also ≥ 500 msec. Changes from Baseline will be defined as the change between QTcF post-dose from the time-matched average Baseline triplicates on Baseline Day 1 (Visit 2).

The study drug will be administered under the supervision of study personnel, which should eliminate the opportunity for abuse during the course of the study. However, Investigators should take note of AEs that might suggest that the study drug has the potential for abuse. For example, the occurrence of a euphoria-like response is a key observation in the clinical assessment of whether a test drug has abuse potential.

Examples of Medical Dictionary for Regulatory Activities (MedDRA) Preferred Terms that may provide abuse-related information about a drug include:

- Euphoria-related terms - euphoric mood, elevated mood, feeling abnormal, feeling drunk, feeling of relaxation, dizziness, thinking abnormal, hallucination, inappropriate affect
- Terms indicative of impaired attention, cognition, and mood - somnolence, mood disorders, and disturbances
- Dissociative/psychotic terms - psychosis, aggression, confusion, and disorientation
- Drug withdrawal syndrome

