7.4 Follow-Up of Adverse Events and Serious Adverse Events

All unresolved AEs will be followed for up to a minimum of *14 days* after the patient's final dose of study drug on Day 7 unless the Investigator's judgment dictates otherwise, the event has resolved or stabilized before Day 21, or the patient is lost to follow-up.

All AEs that result in discontinuation and all SAEs will be followed until one of the following occurs:

- The event resolves.

- The event stabilizes.
- The event returns to a Baseline value, if a Baseline value is available.
- The event can be attributed to agent(s) other than the study drug or to factors unrelated to study conduct.

When it becomes unlikely that any additional information can be obtained (e.g., patient or health care practitioner refuses to provide additional information, the patient is lost to follow-up), the Investigator or designee will ensure that the follow-up includes any pertinent supplemental investigations (e.g., laboratory tests or investigations, histopathological examinations, or consultation with other health care professionals) to elucidate the nature and/or causality of the AE or SAE.

Investigators are not obligated to actively seek AEs or SAEs in former study patients that occur after the Follow-Up Period. However, if the Investigator or designee learns of any AE or SAE at any time after a patient has been discharged from the study and the event is considered as reasonably related to the study drug, the Investigator will notify Relmada.

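### Section 4.5 restates a QTcF stopping trigger as a condition for ending repeat ECGs, so repeats may end while QTcF is still at trigger level

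*Combined protocol and SAP*

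**What the plan says.** The stopping rule in Section 4.5 has two limbs joined by 'or': QTcF of 500 msec or more, or a rise of 60 msec or more over the patient's Baseline. A patient who meets either "will discontinue study medication and be re-assessed". The next sentence says how long repeats go on: "The ECG should be repeated until values return below 500 msec, or ≥ 60 msec above Baseline". A cardiologist then reviews the findings, and any further intervention is discussed with the Medical Monitor and the Sponsor.

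The revised-text column of the Amendment 3 table (Section 11.13) carries the same repeat sentence, so the wording is not a fault of text extraction. Amendment 4 (Section 11.14) changed QTc to QTcF in this bullet, and the current protocol still has the repeat sentence as it was.

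Section 7.1.4 uses the same two limits for a QTcF adverse event of interest, there for a rise over the patient's "Baseline value that continuously occurs over a period of time". It gives no rule for ending repeats.

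**The concern.** An end rule should be the reverse of the rule that starts the action. Here one limb is reversed (at or above 500 becomes below 500) and the other is not. A site that follows the sentence could end repeat ECGs in a patient whose QTcF still meets the criterion that stopped the drug.

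The rule matters in this trial. Safety is the primary objective. Section 1.1.1 reports that d-methadone blocks hERG more potently than l-methadone (IC50 2 against 7 µM). Day 1 uses loading doses of 75 or 100 mg, and the multiple-dose study summarised in Section 1.2.2 showed large accumulation, so exposure need not fall quickly once dosing stops. About 10 sites have to apply the clause in the same way.

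**Working it through.** The plan gives no figure to reproduce, so the check is of the rule's logic.

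**Inputs.** B is Baseline QTcF and Q is QTcF at a repeat ECG, both in whole msec.
- Trigger (Section 4.5): Q ≥ 500 or Q ≥ B + 60.
- Range of B: entry is barred at an average QTcF of 450 msec or more "from the 12-lead ECGs performed at Screening" (Section 4.3). I assume that B stays below 450. The values 380, 400 and 420 used below are illustrative assumptions.

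**1. As written.** Repeats end if Q < 500 or Q ≥ B + 60. They must continue only if Q ≥ 500 and Q < B + 60. For B ≤ 440, B + 60 ≤ 500, so no value of Q meets both and the sentence never requires a further repeat. For B from 441 to 449, repeats must continue only from 500 to B + 59: at 500 alone for B = 441, and from 500 to 508 for B = 449. So the sentence as printed does not work as an end rule.

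**2. Sign corrected, 'or' kept.** Repeats end if Q < 500 or Q < B + 60. For B < 440, the values that still meet the trigger but allow repeats to end run from B + 60 to 499:

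| Assumed B | Band (msec) | Largest rise still allowed |
|---|---|---|
| 380 | 440 to 499 | 499 − 380 = 119 |
| 400 | 460 to 499 | 499 − 400 = 99 |
| 420 | 480 to 499 | 499 − 420 = 79 |

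At B = 440 the band is empty. For B from 441 to 449 it reappears above 500, from 500 to B + 59 (500 to 508 at B = 449).

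**3. Each limit cleared separately ('respectively').** A patient who breached one limit must clear that limit, and a patient who breached both must clear both. Repeats then end when Q < min(500, B + 60), and no triggering value qualifies.

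**4. Both limits joined by 'and'.** Repeats end if Q < 500 and Q < B + 60, which is again Q < min(500, B + 60). No triggering value qualifies at any Baseline.

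Readings 3 and 4 give the same result. Reading 3 needs a reversed comparison and an unstated 'respectively'. Reading 4 says it outright.

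**The case against.** The best defence is that no cardiologist or ECG reader would apply the sentence literally. It names the two limits in the same order as the trigger and speaks of values returning, so the natural repair is that each breached limit must be cleared. On that reading nothing goes wrong. It is probably what the sponsor meant, but the text does not say it, and a safety rule used at about 10 sites should not depend on it.

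The second defence is the other protection in the protocol, and much of it stands:
- Dosing has stopped and a cardiologist reviews the findings (Section 4.5).
- For patients who stop drug early, "all EDP assessments should be completed" (Section 6.1.4), at least 2 more inpatient days follow (Section 6.1.6), and every effort is to be made to perform the Day 14 assessments (Section 4.5). Table 1 includes an ECG at both EDP and Day 14.
- The Investigator may add ECGs at any time (Section 6.2.4).
- The Synopsis (Procedures, Safety), in a paragraph that names ECGs, has clinically significant abnormalities followed until they resolve or stabilise. Section 7.4 follows adverse events that cause discontinuation to one of several endpoints, such as "The event returns to a Baseline value, if a Baseline value is available".

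These limit the harm, but none states a QTcF value for ending repeats. Both follow-up rules also allow follow-up to end at stabilisation, which could be a raised plateau. Section 4.5 adds that after a patient's discontinuation "PK and safety assessments may continue at the discretion of the Investigator". That sentence concerns patient discontinuation and does not clearly override the provisions for patients who stop study drug only, so I give it little weight.

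A reader might infer that the protocol requires no repeat ECG, or tells sites to stop monitoring at any QTcF. The documents do not support that. Reassessment is required, which implies at least one repeat; the sentence sets how long repeats should run and does not forbid more; and the literal reading is one that few clinicians would apply.

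**Conclusion.** The clause is wrong as written. It is a drafting error in an operative cardiac-safety rule, not a deliberate design choice. The size that matters in practice comes from the sign-corrected reading: repeats may end anywhere from 60 msec above Baseline up to 499 msec, which is 460 to 499 msec at an assumed Baseline of 400. This rests on keeping the printed 'or' and on not supplying the unstated 'respectively'. The bands describe what the rule permits; they say nothing about how often patients would fall in them.

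The point should not be carried further. A reader might infer that patients stay on drug with a prolonged QTcF, or that the safety results would be biased. Neither follows: the stopping trigger itself is sound, and no planned analysis uses the repeat clause. Both Phase 1 studies reported no clinically significant QTcF prolongation (Sections 1.2.1 and 1.2.2). The correction should be made because the rule is in operation and the change is small, not because harm is expected.

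**What to change.** In Section 4.5, replace the end condition of the repeat-ECG sentence with: *until QTcF is below 500 msec and less than 60 msec above Baseline*. This is the exact complement of the sponsor's own trigger.

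Do not add a definition of Baseline in the same edit. Table 1, footnote a, says "All Baseline/Day 1 assessments and activities will be done pre-dose, unless otherwise specified", which might suggest a pre-dose Day 1 value. But Section 7.1.4 measures QTcF change from a time-matched Day 1 average, and the Synopsis (Statistical Data Analysis) and Section 8.1.4.3 summarise ECG change from Check-in on Day -1. Naming one here would choose among them, and that is a separate decision.

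The cost is one clause. The scheduled ECGs, sample size and planned analyses do not change. Some patients who meet the trigger may need more unscheduled repeats than the present wording requires.

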2 STUDY OBJECTIVES

2.1 Primary Objective

The primary objective of this study is safety:

Safety objectives will assess the safety and tolerability of 25 mg and 50 mg of REL-1017 (d-methadone) compared to Placebo as adjunctive treatment in patients with MDD. The following assessments will be conducted to measure safety and tolerability throughout the study:

- AEs
- Vital signs
- Weight
- Physical examination
- Clinical laboratory parameters (chemistry, hematology, and urinalysis)
- Electrocardiogram (ECG) parameters
- Columbia-Suicide Severity Rating Scale (C-SSRS)
- Clinician Administered Dissociative States Scale (CADSS)
- Clinical Opiate Withdrawal Scale (COWS)
- 4-Item Positive Symptom Rating Scale (4-Item PSRS)

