6.1.6 Discharge (Day 9)

Following the last dose of study drug, each patient (including those who discontinue from the study drug prior to Day 7) is to remain in the inpatient facility for at least 2 additional days of safety and efficacy monitoring. The assessments to be conducted prior to Discharge on Day 9 are listed in the Time and Events Schedule (Table 1). Blood samples will also be drawn for PK analysis prior to Discharge on Day 9.

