6.1.7 Outpatient Observation Period (Day 10 to Day 14)

The End of the Observation Period (EOP) will occur on Day 14 when the EOP interview will be conducted in person to assess psychiatric symptoms and safety endpoints, including medical conditions, new medications, and newly emergent AEs as listed in the Time and Events Schedule (Table 1). A confirmatory pregnancy test will be administered. Blood samples will also be drawn for PK analysis approximately 168 hours after the last dose of study drug. For patients who discontinue study drug prior to Day 7, the EOP interview will occur 7 days after their last dose of study drug. (The window for the EOP visit is ± 3 days.)

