6.1.8 Follow-Up Period (Day 15 to Day 21)

Follow-up interviews will be conducted with all patients (including those who discontinue from the study drug prior to Day 7) 14 days after their last dose of study drug. (The visit window is ± 3 days). In the Follow-Up interview (Day 21), C-SSRS, AEs, and medications will be recorded (Table 1). This interview may be conducted by telephone. A confirmatory pregnancy test will be administered if the visit is conducted at the site. During the Follow-Up Period, safety evaluations should be conducted, at the discretion of the Investigator, to evaluate any unresolved abnormal treatment-emergent findings.

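### Section 4.5 makes PK and safety assessments after discontinuation discretionary where 6.1.4, 6.1.6 and 6.1.8 require them, so scheduled Day 7–9 data and the Day 21 C-SSRS could be selectively missing

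*Combined protocol and SAP*

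**What the plan says.** Section 2.1 puts safety first: "The primary objective of this study is safety". Two parts of the protocol then say what is collected from a patient who stops early.

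Section 4.5 (discontinuation and withdrawal):
- Once a dosed patient has discontinued, "PK and safety assessments may continue at the discretion of the Investigator", using the Table 1 time points.
- The paragraph before it covers premature discontinuation for any reason after dosing. There the investigator "must make every effort to perform the assessments scheduled for the Day 14 visit", set at 7 days after the last dose.

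Section 6.1 (study procedures; the synopsis repeats the early-stopper rules):
- 6.1.4: "For patients who discontinue study drug prior to Day 7, all EDP assessments should be completed", unless consent has been withdrawn.
- 6.1.5: "On Day 8, patients will be evaluated 24 hours after the final dose of study drug on Day 7". Early stoppers are not mentioned.
- 6.1.6: each patient, early stoppers included, "is to remain in the inpatient facility for at least 2 additional days of safety and efficacy monitoring".
- 6.1.7: for early stoppers, "the EOP interview will occur 7 days after their last dose of study drug".
- 6.1.8: "Follow-up interviews will be conducted with all patients (including those who discontinue from the study drug prior to Day 7", at 14 days after the last dose. C-SSRS, AEs and medications are recorded.

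**The concern.** A site that follows 4.5 and a site that follows 6.1 would collect different data from the same kind of patient, and both could claim to comply.

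The circumstances for discontinuation in 4.5 include intolerable AEs, clinically significant ECG, vital-sign, laboratory or examination findings, and raised ALT or AST. The discretion therefore falls on the patients who tell most about the primary objective. If an investigator's choice to continue assessments is related to how the patient is doing, the missing values depend on the outcome.

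Dosed patients are not replaced (4.5). Section 8.1.7 names a missing-data method for efficacy only and leaves further detail to the SAP.

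**Working it through.** The plan has no figure to reproduce here: Section 8.2 makes no formal sample size calculation, and no dropout rate is given. The check is mainly textual.

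**Step 1. Do the rules reach the same patients?** Section 6.1 speaks of stopping study drug. Section 4.5 speaks mostly of leaving the study, but its list of study-discontinuation circumstances includes a QTcF rule whose consequence is to stop study medication and re-assess. The discretionary sentence names neither the study nor the drug. A patient who stops drug for an AE and keeps consent in place can fall under both.

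**Step 2. Compare section by section.**
- 6.1.4 (end-of-dosing assessments): conflicts with 4.5.
- 6.1.5 (Day 8): no conflict shown, because it is silent on early stoppers.
- 6.1.6 (two further inpatient days): conflicts with 4.5.
- 6.1.7 (Day 14): no conflict, because 4.5 asks for the same visit in firm terms.
- 6.1.8 (follow-up interview): conflicts for the C-SSRS. AE recording to Day 21 is separately required by Section 7.

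**Step 3. Which data depend on the conflict?** From Table 1:

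| Item | Days 7–9 | Day 14 | Day 21 |
|---|---|---|---|
| CADSS, 4-Item PSRS | 7, 9 | no | no |
| Physical examination | 7, 9 | no | no |
| ECG, vital signs, PK | 7, 8, 9 | yes | no |
| Laboratory tests | 7 | yes | no |
| COWS | 8, 9 | yes | no |
| C-SSRS | 8, 9 | yes | yes |

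Under 4.5 alone, only the Day 14 column is firm. For the first two rows that leaves nothing after the stop. CADSS and PSRS are otherwise measured only on Day 1, and the physical examination only before dosing. For the other rows, the Day 7–9 values are exposed but a Day 14 value is protected. The Day 21 C-SSRS is exposed.

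**Step 4. Size, for illustration.** Inputs: n = 20 per arm (8.2) and d = 1 to 4 patients per arm unassessed on an exposed item (assumed).

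If none of the 20 − d assessed patients has an event, the arm's rate lies between 0/20 and d/20:
- d = 1: 0 to 1/20 = 5%
- d = 2: 0 to 2/20 = 10%
- d = 3: 0 to 3/20 = 15%
- d = 4: 0 to 4/20 = 20%

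If the loss is unrelated to outcome, the cost is only in detection. The chance of at least one event is 1 − (1 − p)^n:
- p = 0.10: 1 − 0.90^20 = 0.878, against 1 − 0.90^16 = 0.815
- p = 0.05: 1 − 0.95^20 = 0.642, against 1 − 0.95^16 = 0.560

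**The case against.** The best reply is that the two sections describe different situations. A patient off drug but still in the study follows 6.1. A patient who has left the study gets Day 14 plus whatever the investigator can still arrange. On that reading nothing conflicts.

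There are also real safeguards outside the disputed sentence:
- 4.5 itself asks for the Day 14 set, which includes ECG, vital signs, laboratory tests, C-SSRS, COWS and PK.
- Section 7 has all AEs recorded to Day 21. Section 7.4 has AEs leading to discontinuation, and all SAEs, followed to a defined end.
- Section 7.1.3 turns clinically significant abnormal findings that meet the definitions into AEs.
- After a QTcF stop, 4.5 requires repeat ECGs and cardiology review.
- Study staff are blinded, which limits any route to loss that differs by arm.

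The safeguards stand, and they narrow the point to the items in Step 3. The separation of situations does not stand as written: 4.5 never draws it, and its QTcF rule mixes the two. Even if it were drawn, a patient whom the investigator removes for an AE, with consent intact, would still come under discretion. Section 7.1.3 helps only where the assessment is made.

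On blinding, Section 5.6 withdraws a patient after a code break, so discretion could then be used with treatment known. That is a narrow case. A reader might infer from it that missingness will differ by arm, but the documents give no evidence of that.

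**Conclusion.** The concern holds in a limited form. A stated rule, not merely an absent detail, allows the end-of-dosing and discharge assessments (CADSS, 4-Item PSRS, physical examination, routine ECG, vital signs, laboratory tests, COWS, C-SSRS and PK) and the Day 21 C-SSRS to be skipped selectively in patients who stop for safety reasons. The loss is most complete for CADSS, PSRS and physical examination.

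A reader might go further and infer that the primary safety data as a whole are left to investigators' choice, or that everything from 6.1.4 to 6.1.8 contradicts 4.5. The documents support neither: core AE and SAE capture is mandatory, Day 14 is protected in both places, and 6.1.5 makes no demand for early stoppers.

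The upper limits of 5% to 20% rest on an assumed 1 to 4 unassessed patients per arm and on every one of them having the event. They show what the data could not rule out and do not estimate bias.

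**What to change.** Reconcile the discretionary sentence in 4.5 with 6.1.4, 6.1.6 and 6.1.8:
- State whether it applies to stopping study drug, leaving the study, or both.
- For patients who stop drug and have not withdrawn consent, have 4.5 refer to the data collection already scheduled in 6.1. Limit discretion to additional unscheduled tests, much as 6.1.8 already does for unresolved findings.
- State separately what is collected from patients who leave the study, including after a code break.
- State what applies on Day 8 for early stoppers.

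The cost is a few sentences. The change to 4.5 adds no visits beyond those 6.1 already requires; Day 8 is left for the sponsor to specify. The request concerns data collection and consistency between sections. It proposes no change to clinical management and takes no position on stopping rules or length of stay.
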